3.3 Exploratory endpoints

- The expression levels of PD-L-1 in tumor tissue, and immunologic markers as well as serum titers of hepatitis B or C in patients with hepatitis B or C, respectively, for whom specimens are available.

3.3.1 Evaluable:

- Evaluable for Tissue Correlative Study: Eligible subjects who agree to tissue sampling, receive at least one dose of pembrolizumab, have measurable disease at baseline, and have at least one post-baseline disease response assessment.
- Evaluable for Serum Correlative Study: Eligible subjects who agree to serum sampling and receive at least one dose of pembrolizumab.

4.0 **SUBJECT RECRUITMENT & SCREENING**

Subjects will be recruited at Sylvester Comprehensive Cancer Center via clinical practice offices. Both men and women of all races and ethnic groups are eligible for this trial.

5.0 **PATIENT SELECTION**

5.1 **Inclusion Criteria**

1	Patients must have diagnosis of advanced hepatocellular cancer (HCC) by one of the following: a) Histopathology b) Elevated serum alpha-fetoprotein (AFP) >400 ng/ml and findings on magnetic resonance imaging (MRI) or computed tomography (CT) scans characteristic of HCC c) Findings on triple phase MRI or CT scans characteristic of HCC in patients with cirrhosis and tumors at least 1 cm or greater, without a curative treatment option (transplant, resection, or ablation).
2	Measurable disease as defined by RECIST v1.1 (provided in Section 14.0).
3	Radiographic progression on previously treated areas (as defined by RECIST v1.1).
4	Subject refusal for sorafenib treatment or intolerance to sorafenib are also allowed (intolerance is defined as ≥ 28 days of sorafenib (not necessarily consecutive) or \geq grade 3 toxicity due to sorafenib which does not resolve with appropriate supportive care).
5	Patients should have failed at least one prior systemic therapy regimen which could include sorafenib. Patients may have progressed on sorafenib, been intolerant of, or refused sorafenib. Patients who are documented to refuse systemic chemotherapy or sorafenib are also eligible. No limit to prior systemic therapy. Prior locoregional therapy such as surgery, radiofrequency ablation or transarterial chemoembolization are also allowed, provided that progression has been documented after these therapies, and ≥ 4 weeks have elapsed since the last therapy; (these will not be counted as systemic therapy).
6	Child-Pugh Classification with score ≤ 7 points. See Appendix G for criteria.

7	Age \geq 18 years
8	Estimated life expectancy, in the judgement of the Investigator, of at least \geq 12 weeks.
9	ECOG performance status of 0 or 1. See Appendix C.
10	Adequate bone marrow function as defined below: a) absolute neutrophil count (ANC) \geq $1.2 \times 10^9/L$, b) platelets (PLT) \geq $50 \times 10^9/L$
11	Adequate liver function as defined below: a) serum bilirubin $<$ 2 mg/dl b) AST(SGOT) \leq 5 x ULN, c) ALT(SGPT) \leq 5 x ULN
12	Adequate coagulation as defined by: a) serum prothrombin time (PT) \leq 16 seconds
13	Adequate renal function as defined by one of the following: a) serum Creatinine \leq 1.5 x ULN OR b) (measured or calculated) Creatinine clearance \geq 60 mL/min for patients with serum creatinine levels $>$ 1.5 x ULN.
14	Suitable venous access to allow for all study-related blood sampling.
15	Female subject of childbearing potential (CBP) must have a negative urine or serum pregnancy within 3 days prior to receiving the first dose of study medication.
16	Females of child bearing potential that are sexually active must agree to either practice 2 medically accepted highly effective methods of contraception at the same time or abstain from heterosexual intercourse from the time of signing the informed consent through 120 days after the last dose of study drug. See Appendix H for protocol-approved highly effective methods of contraceptive combinations. Subjects of childbearing potential are those who have not been surgically sterilized or have not been free from menses for $>$ 1 year.
17	Negative test for pregnancy is required of females of child-bearing potential; A female of child bearing potential is any woman, regardless of sexual orientation or whether they have undergone tubal ligation, who meets the following criteria: a) has not undergone a hysterectomy or bilateral oophorectomy; or b) has not been naturally postmenopausal for at least 24 consecutive months (i.e., has had menses at any time in the preceding 24 consecutive months or 730 days).
18	Conception while on treatment must be avoided
19	Male subjects should agree to use an adequate method of contraception starting with the first dose of study therapy through 120 days after the last dose of study therapy.
20	Ability to understand and willingness to sign a written informed consent document.

5.2 Exclusion Criteria

1	Active autoimmune disease that has required systemic treatment in the past 2 years (i.e. with use of disease modifying agents, corticosteroids or immunosuppressive drugs). Replacement therapy (e.g., thyroxine, insulin, or physiologic corticosteroid replacement therapy for adrenal or pituitary insufficiency, etc.) is not considered a form of systemic treatment.
2	Diagnosis of immunodeficiency or is receiving systemic steroid therapy or any other form of immunosuppressive therapy within 2 years prior to the first dose of trial treatment.
3	Major surgical procedure within 28 days prior to enrollment. Note: If subject received major surgery, they must have recovered adequately from the toxicity and/or complications from the intervention prior to starting therapy.
4	Any unresolved toxicity > CTCAE grade 2 despite optimal care/support, from previous anti-cancer therapy, within 28 days prior to first dose of study drug. [Exceptions: Alopecia and \leq grade 2 neuropathy.]
5	Prior therapy with an anti-PD-1, anti-PD-L1, or anti-PD-L2 agent.
6	Receipt of anti-cancer monoclonal antibody within 4 weeks prior to first dose of study drug.
7	Prior treatment with any other chemotherapy, radiotherapy, immunotherapy, or anticancer drug, agent or biologic within 4 weeks prior to first dose of study drug.
8	Has received a live vaccine within 30 days of planned start of study therapy. Note: Seasonal influenza vaccines for injection are generally inactivated flu vaccines and are allowed; however intranasal influenza vaccines (e.g., Flu-Mist®) are live attenuated vaccines, and are not allowed.
9	Receipt of any other investigational agents for their cancer \leq 4 weeks of the first dose of study treatment.
10	Known history of active TB (Bacillus Tuberculosis).
11	Known history of, or any evidence of active, non-infectious pneumonitis or has a history of (non-infectious) pneumonitis that required steroids or current pneumonitis.
12	Known history of Human Immunodeficiency Virus (HIV), HIV1/2 antibodies.
13	Known hypersensitivity to pembrolizumab or any of its excipients.
14	Known active central nervous system (CNS) metastases and/or carcinomatous meningitis. [Exception: Subjects with previously treated brain metastases may participate provided they are stable (without evidence of progression by imaging, for at least 4 weeks prior to the first dose of study drug and any neurologic symptoms have returned to baseline), have no evidence of new or enlarging brain metastases, and are not using steroids for at least 7 days prior to trial treatment. This exception does not apply to carcinomatous meningitis which is excluded regardless of clinical stability.]

15	Is pregnant or breastfeeding, or expecting to conceive or father children within the projected duration of the trial through 120 days after the last dose of trial treatment.
16	Any uncontrolled, intercurrent illness including but not limited to ongoing or active infection, symptomatic congestive heart failure, unstable angina pectoris, cardiac arrhythmia.
17	Has a known additional malignancy that is progressing or requires active treatment. [Exception: Basal cell carcinoma of the skin or squamous cell carcinoma of the skin that has undergone potentially curative therapy, or in situ cervical cancer.]
18	Any other serious medical or psychiatric illness/condition likely in the judgment of the Investigator(s) to interfere or limit compliance with study requirements/treatment.
19	Treatment for active HCV within 60 days of study entry. [Note: Untreated HCV positive subjects are eligible, and if stable on pembrolizumab for 6 months after study entry, consideration may be given to starting anti-HCV therapy, at the discretion of the treating Investigator.]
20	HCC patients with evidence of prior HBV must fulfill the following criteria in order to be eligible for the study: HBV VL <100 IU/mL before study enrollment, and subjects with active HBV need to be on anti-HBV suppression ≥ 3 months, throughout treatment and for 6 months after.

6.0 Enrollment Procedures

To enter a patient, the Investigator or Study Team will contact the Clinical Research Services' (CRS) Representative. All eligibility requirements must be reviewed prior to the patient entering the study. The following information must be provided to the CRS Representative:

- 1) Completed and signed protocol-specific eligibility checklist;
- 2) All pages of the original signed informed consent form (ICF) including HIPAA Form B;
- 3) Relevant source documents including but not limited to: subject medical history and physical exam, concomitant medications, admission or discharge notes, diagnostic reports, pathologic confirmation of diagnosis, and relevant subject-specific written communication.

6.1 Cancellation Guidelines

Patient may withdraw from the study at any time. Contact the CRS Representative, or e-mail the information including the reasons for withdrawal within 10-business days.

7.0 STUDY DESIGN

The study will be an open-label, single-institution, non-randomized, single-arm, Phase II study of pembrolizumab therapy in patients with advanced HCC. Patients will be treated in three-week cycles, with intravenous (IV) administration of pembrolizumab on day 1 of each 3-week cycle. Trial therapy will last until withdrawal of consent, disease progression and/or unacceptable toxicity, whichever occurs first.

Correlative studies investigating PD-L-1 expression in tumor tissue will be assessed with clinical outcome. Peripheral blood will also be drawn to perform immunologic markers and hepatitis B or C viral titers. This is to determine if viral titers change with treatment. These studies are included for all patients who consent to the correlative studies (See Appendix F). There is an additional consent for the correlative studies.

Up to 28 evaluable patients will be enrolled at Sylvester Comprehensive Cancer Center (SCCC). We expect to enroll 10-12 patients per year based on our institution's enrollment capacity. Expected time to complete total accrual is approximately 1.5 years. Expected time to study completion is 3 years from date open to enrollment to allow for survival data. An interim analysis is planned after 14 evaluable patients are assessed for DCR to determine whether to continue with an additional 14 more.

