Follow-up Required Post-Treatment	All subjects will be followed at approximately 30-days (+5 days) after the last dose of trial treatment or before the initiation of a new anti-cancer treatment, whichever occurs first. For subjects without documented evidence of objective disease progression a telephone call to the subject and/or the subject’s family may be made every 12 weeks to evaluate the patient’s status until documented disease progression, death, withdrawal of consent, or end of study, whichever occurs first.																																																																			
Objectives	
Primary Objectives:
 
 To determine the disease control rate (CR, PR, or SD) and response rate (CR and PR) of pembrolizumab in patients with advanced HCC. To determine the safety of pembrolizumab in HCC patients. 
Secondary Objective:
																																																																			

	
 • To determine the progression-free survival (PFS), overall survival (OS), objective response rate (ORR), and duration of response (DOR). 
Exploratory Objective(s):
 
 • To assess HCC tumor specimens (if available) for PD-L-1 expression, and correlate with response to therapy. • To assess immunologic markers (if serum, available) for response. • To assess changes in hepatitis B and/or hepatitis C viral titer loads with pembrolizumab treatment for HCC.
Expected Number of Patients	35
Expected Number of Centers	Single center: Sylvester Comprehensive Cancer Center (SCCC). Note: SCCC is inclusive of the constituent satellite sites.
Expected Duration of the Protocol	
Estimated duration of the main protocol (e.g. from start of screening to last subject processed and finishing the study): 3 years. This includes long term follow-up of patients, some of whom may have durable responses to therapy.
 
Patient accrual is expected to be completed in 1.5 years (18 months). Planned accrual goals include 10-12 subjects within 1 year.

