3.2 Secondary endpoints

- Progression-free survival (PFS) will be defined as the elapsed time from the first date of study treatment until documented disease progression (as per RECIST 1.1) or death from any cause, whichever is earlier. For patients who remain alive without progression, follow-up time will be censored at the date of last disease assessment (as per RECIST 1.1).
- Overall survival (OS) will be defined as the elapsed time from the first date of study treatment to death from any cause. For surviving patients, follow-up will be censored at the date of last contact (or last date known to be alive). Follow-up for OS will occur every 12 weeks (± 1 month) until death or withdrawal of consent from the study.
- Objective response rate (ORR) will be defined as the proportion of the patients with a confirmed complete or partial response (CR or PR), as per RECIST 1.1.
- Duration of Response (DoR) will be defined as the elapsed time from documented tumor response to documented disease progression.

- 3.2.1 Evaluable for PFS, OS, ORR and DOR: Eligible subjects who receive at least one dose of pembrolizumab, have measurable disease at baseline, and have at least one post-baseline disease response assessment.

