12.5 Follow-up Evaluations

For patients without documented evidence of objective disease progression the following assessments should be performed every 12 weeks until documented disease progression, death, withdrawal of consent, or end of study, whichever occurs first. A *telephone call* to the patient and/or the patient's family may be made to evaluate the patient's status on the following:

- Post-study anticancer therapy status
- Survival status
- Following confirmed disease progression or initiation of new anti-cancer therapy, survival will be assessed (at a minimum) by telephone contact every 12 weeks (± 2 weeks)."

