16.4 Patient Enrollment and Study Duration

We plan to enroll up to 35 patients, to ensure that we have a minimum of 28 patients who are evaluable for the primary efficacy endpoint for this study, disease control rate (DCR). We expect to enroll 10-12 patients per year based on our institution's enrollment capacity.

Accrual will be suspended after 14 evaluable patients (stage 1) in order to assess DCR in accordance with the two-stage design of this trial.

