The Kaplan-Meier method will be used to estimate progression-free and overall survival rates and corresponding median times, if attained. Point estimates with corresponding 95% confidence intervals based on Greenwood's variance and the log-log transform method will be given for the proportion of progression-free/surviving patients at selected times, such as 3, 6, 12, 18, and 24 months following the initiation of treatment, as well as for median times, if attained [41]. For purposes of these analyses, progression-free survival will be measured from start date of treatment to date of documented disease progression, or death from any cause, whichever occurs first. Patients who are alive and progression-free will be censored at their date of last documented progression-free status. Overall survival will be measured from start date of treatment to date of death from any cause. Patients who are alive will be censored at their date of last contact. To the extent possible with 28 patients, we will explore the effect of baseline characteristics on progression-free and overall survival using Cox regression [42]. The objective response rate (ORR) will be estimated by the percentage of patients and corresponding 95% confidence interval using the exact binomial method.

To the extent that biomarker data are available, we will summarize expression levels of PD-L- 1 in tumor tissue, and serum titers of hepatitis B and/ hepatitis C in patients with hepatitis B or C, respectively, using descriptive statistics. A descriptive analysis will be done for hypothesis-generating purposes but a statistical analysis will not be done as there may not be enough tumor tissue and blood samples collected (to conduct a formal statistical analysis).

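### The stated accrual rate of 10-12 patients per year cannot give 28 evaluable patients in 1.5 years: it gives 15-18, and 28 take 28.0-33.6 months; separately, duration of response has no rule for ongoing responses

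*Combined protocol and SAP*

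**What the plan says.** Section 7.0 gives a ceiling of 28 evaluable patients and then: "We expect to enroll 10-12 patients per year based on our institution's enrollment capacity. Expected time to complete total accrual is approximately 1.5 years". It continues: "Expected time to study completion is 3 years from date open to enrollment to allow for survival data".

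The synopsis (Expected Duration of the Protocol) has the same 18 months with a slightly different statement of pace: "Patient accrual is expected to be completed in 1.5 years (18 months). Planned accrual goals include 10-12 subjects within 1 year". It lists 35 expected patients and an estimated duration of 3 years.

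Section 16.4 repeats the yearly rate and adds "We plan to enroll up to 35 patients, to ensure that we have a minimum of 28 patients who are evaluable". It also says "Accrual will be suspended after 14 evaluable patients (stage 1) in order to assess DCR". The length of that suspension is not given.

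On follow-up, section 12.5 has patients without progression followed "until documented disease progression, death, withdrawal of consent, or end of study, whichever occurs first", while section 3.2 has overall survival (OS) followed "until death or withdrawal of consent from the study". Section 16.5 plans Kaplan-Meier estimates of progression-free survival (PFS) and OS "at selected times, such as 3, 6, 12, 18, and 24 months following the initiation of treatment".

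Duration of response (DOR) is defined in the abbreviations table, section 3.2 and section 14.5.5 as ending at documented progression (14.5.5 adds recurrence). Section 14.5.5 also ends the duration of stable disease (SD) at progression. Section 16.5 reports both by median and range; it specifies Kaplan-Meier only for PFS and OS.

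**The concern.** The sample size, the yearly rate and the accrual time stand together in section 7.0 and cannot all be true. The accrual time matters because the 3-year completion is justified by the need for survival data. Eighteen months of accrual inside 36 months would leave every patient at least 18 months of potential follow-up. Slower accrual uses up most of that margin for the patients who enter last. If the analysis were done at month 36, the 18- and 24-month estimates would rest on fewer patients and more responses would still be ongoing.

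The DOR gap is a separate matter and does not arise from the accrual rate. A plain median and range needs a completed duration for each patient. Nothing says what value a patient still in response contributes, or how death without progression is treated, so two analysts could report different DOR results from the same data.

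**Working it through.** **Inputs.** Rate 10-12 per year (7.0, 16.4); 28 evaluable patients (7.0); up to 35 enrolled (16.4); accrual 18 months (7.0, synopsis); completion at 36 months (7.0).

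**Does 18 months reproduce?**
- Patients in 1.5 years = 1.5 × rate: 1.5 × 10 = 15; 1.5 × 12 = 18. Not 28.
- Months for 28 = 28 / rate × 12: 28/12 × 12 = 28.0; 28/10 × 12 = 33.6. Not 18.
- Rate needed for 28 in 1.5 years: 28/1.5 = 18.7 per year.
- Stage 1 alone (14 patients) takes 14.0-16.8 months and would fit, but the text speaks of total accrual.
- If all 35 enrolments count against the rate: 35/12 × 12 = 35.0 months; 35/10 × 12 = 42.0 months.

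**First-year-goal reading of the synopsis.** If 10-12 is only the first-year target, 28 − 12 = 16 to 28 − 10 = 18 patients must enter in the last 6 months. That is 2.7-3.0 per month, against 10/12 to 12/12 = 0.8-1.0 in year one.

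**Potential follow-up if data were cut at month 36** (28 patients, uniform accrual over A months, no pause):

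| Quantity | Formula | A = 18 (as stated) | A = 28.0 | A = 33.6 |
|---|---|---|---|---|
| Last patient, months | 36 − A | 18 | 8.0 | 2.4 |
| Median, months | 36 − A/2 | 27.0 | 22.0 | 19.2 |
| Patients able to reach 18 months | 28 × 18/A, at most 28 | 28 | 18 | 15 |
| Patients able to reach 24 months | 28 × 12/A | 18.7 | 12 | 10 |

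Each month of pause before stage 2 takes one more month from the last patient.

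**Precision.** Assumptions not in the documents: exponential OS with median 8-16 months, uniform accrual, no loss to follow-up. The large-sample Greenwood standard error is S(t) × √(∫₀ᵗ λ / [n S(u) G(u)] du). Here n = 28, λ = ln 2 / median, S(u) = exp(−λu), and G(u) = min(1, (36 − u)/A) is the proportion with potential follow-up of at least u.

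| OS median (months) | SE of S(24): A = 18 | A = 28.0 | A = 33.6 | Ratios to A = 18 |
|---|---|---|---|---|
| 8 | 0.066 | 0.078 | 0.085 | 1.18, 1.28 |
| 12 | 0.085 | 0.099 | 0.108 | 1.16, 1.26 |
| 16 | 0.094 | 0.108 | 0.117 | 1.15, 1.25 |

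The 24-month standard error is thus about 15-28% larger. The increase is 8-19% at 18 months and 2-9% at 12 months. With median 12, the expected number at risk at 24 months is 28 × 0.25 × 12/A: 4.7 for A = 18, 3.0 for A = 28.0 and 2.5 for A = 33.6.

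**Primary design.** Exact two-stage calculation (stop at 2 or fewer of 14, succeed at 9 or more of 28): type I error 0.0495, power 0.905, early stopping 0.526 at 18% and 0.024 at 43%. Section 16.2 states 5%, 90%, 53% and 2%. These do not depend on accrual time.

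**DOR.** The background reports 2 complete and 7 partial responses in 39 patients on another PD-1 antibody. At that rate 28 × 9/39 = 6.5, so about 6 responders would contribute to DOR.

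**The case against.** The strongest objection is that the harm needs a hard data cut at month 36, and no section imposes one. The 3 years is an expected time, OS follow-up under 3.2 runs on, and end of study is never equated with month 36. Even the stated timetable does not fit a hard cut: a patient entering at month 18 and treated for the permitted 24 months would finish at month 42. This stands. A reader might infer from 12.5 that PFS will be truncated at 36 months; the documents do not support that as a fact, only as what would follow if end of study were set there.

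Two other readings also go too far. One is that late entrants as a group would have only 2.4-8.0 months. That range is the last patient alone at the two rates; the median is 19.2-22.0 months. The other is that accrual will take 35-42 months. Thirty-five is a ceiling, and the revision history says it also covers screen failures. The protocol does not say whether its yearly rate counts them, so if the rate counts treated patients only, the time is shorter.

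It is fair, too, that the 18-month comparator is implied (36 − 18) and not promised, that the landmark times are given as examples, and that few patients would be at risk at 24 months under any schedule.

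The first-year-goal reading does not rescue the 18 months. Sections 7.0 and 16.4 both give a yearly rate tied to institutional capacity, and about a threefold acceleration is nowhere explained.

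On DOR, a descriptive range with ongoing cases marked would be a lesser remedy. It still needs a stated rule, and there is none.

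**Conclusion.** The accrual statement in 7.0 and the synopsis is wrong as written: 15-18 patients in 1.5 years, not 28, and 28.0-33.6 months for 28 before the suspension. This needs only the protocol's own numbers, taking every enrolled patient as evaluable, which is favourable to the plan.

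The effect on follow-up is conditional on a cut at month 36. In that case the secondary time-to-event results are less mature, noticeably at 24 months and slightly at 12, on the survival assumptions above. Kaplan-Meier estimates stay valid. A reader might infer that the trial is underpowered or its primary test compromised; it is not, since neither the two-stage rule nor the disease control rate analysis depends on how long accrual takes. The statement should be corrected because it underlies the completion date.

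The missing DOR and SD-duration rule is real but separate, and is a cheap improvement to the analysis plan.

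**What to change.** **Accrual (7.0 and synopsis).**
- Restate accrual as about 2.3-2.8 years for 28 evaluable patients, plus the interim pause; or state the roughly 19 per year that 1.5 years requires and why it is feasible.
- Say whether the yearly rate counts screen failures, and whether the synopsis figure is a rate or a first-year goal.
- Define study completion by a stated minimum follow-up after the last patient's first dose, consistent with OS follow-up in 3.2.

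Cost: wording, a later stated completion date, and staff time if follow-up is extended. Telephone survival contact every 12 weeks is already planned.

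**Duration of response and of stable disease (16.5).**
- Estimate both by Kaplan-Meier, censor ongoing cases at the last disease assessment, and mark ongoing responses as such.
- State how death without progression is handled, and word it identically in the abbreviations table, 3.2, 14.5.5 and 16.5. Counting death as an event changes the endpoint definition, so editing 16.5 alone would create a new contradiction.

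Cost: no new data, but edits in four places. With about 6 expected responders the DOR median will be imprecise.
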